## 7. IMAGE INTERPRETATION

Experienced breast radiologists from our institution will place the Magseed into the axilla and interpret the MRI, mammographic and sonographic imaging as per current clinic practice. This

work flow will remain the same. The non-contrast enhanced breast MRI will be evaluated by both the study investigators and physicists.

## 8. END OF STUDY DEFINITION

A participant is considered to have completed the study once the Magseed has been removed from the axilla.

## 9. SAFETY MONITORING

**Adverse Events (AE):** Adverse event means any untoward medical occurrence associated with the use of an intervention in humans, whether or not considered intervention-related (21 CFR 312.32 (a)).

**Serious Adverse Events (SAE):** An adverse event (AE) or suspected adverse reaction is considered "serious" if, in the view of either the investigator, it results in any of the following outcomes:

- Death
- Life threatening, even if temporary in nature, requiring inpatient hospitalization
- Results in permanent impairment of a bodily function or permanent damage to a body structure
- Necessitates medical or surgical intervention to preclude permanent impairment of a bodily function or permanent damage to a body structure
- Results in an increased level of care (unscheduled admission, transfer from a routine inpatient bed to an intensive care unit, etc.).

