## 6. STUDY RISKS

**Seed Placement:** The Magseed is placed in an axillary lymph node using local anesthesia in an outpatient environment. There is a small risk of discomfort associated with the local anesthetic. There is a minor risk of infection and bleeding or bruising with the needle entry that is similar to a blood draw. Damage to adjacent structures including vessels or the lung are extremely rare with image guidance.

**MRI:** There is no radiation associated with MRI, but patients with metal devices in their body like pacemakers, cannot have an MRI and will not be able to participate in the study.

Patients with claustrophobia may feel trapped in the MRI scanner and may not tolerate the examination. If the patient feels too confined in the MRI scanner the technologist will stop the examination.

The MRI machine makes loud noises, which can damage hearing. Because of this known risk all patients are required to wear ear protection during the MRI scan that will minimize the discomfort and keep the noise levels at a safe level.

Gadolinium is FDA-approved and routinely used for breast MRI exams. Gadolinium can cause discomfort, warm tingling feeling in the body, metallic taste in the mouth, nausea, or headache in about 1 in 100 patients. These side effects usually last only for a very short time and completely resolve. Severe allergic reactions to gadolinium are extremely rare and occur in about 1 in 300,000 people. The needle placed in the patient's vein may cause minor pain, bruising, or infection at the injection site. Studies have shown that small amounts of gadolinium may remain in the body of patients who have received these injections. The effect of this, if anything, is unknown at this time.

Gadolinium may harm a fetus and therefore, pregnant women will not be allowed to enroll on this study. Women of reproductive age will undergo urine pregnancy testing.

Magseed placement will interfere with visualizing the axilla on MRI. The extent to which the artifact could interfere with visualizing the adjacent breast tissue is unknown. This is way phase 1 will consist of ten patients who have already had all their standard breast imaging. The one-time limited non-contrast MRI will allow us to optimize scanning parameters and decrease the artifact for phase 2 participants receiving their standard MRI after Magseed placement.

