**Mammogram:** Inherent risks include added radiation dose. The MQSA (Mammography Quality Standards Act) recommended average glandular dose limit for screening mammography to 3mGy per view, which equals 12 mGy for a standard 4-view mammogram. There is no set limit for average glandular dose for diagnostic mammography. This is because the number of mammographic views for each patient varies based upon the images necessary to work up any particular finding. All diagnostic mammography will be within current clinical guidelines and well below levels that are known to cause long term side effects.

**Magseed:** The Magseed needle contains bone wax, which contains natural beeswax. There is a potential for a very minimal risk for an allergic reaction or a foreign body reaction (granuloma). To further minimize this risk, patients with known allergies to bone wax, beeswax or propolis will be excluded from the study.

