### AE relationship to the study intervention:

- Definitely Related – The AE *is clearly related* to the study intervention.
- Probably Related – The AE *is likely related* to the study intervention.
- Possibly Related – The AE *may be related* to the study intervention.
- Unlikely Related – The AE *is doubtfully related* to the study intervention.

- Not Related – The AE *is clearly NOT related* to the study intervention.

**Expectedness:** Principle investigators and co-investigators will be responsible for determining whether an adverse event (AE) is expected or unexpected. An AE will be considered unexpected if the nature, severity, or frequency of the event is not consistent with the risk information previously described for the study intervention.

- Expected Adverse Events
  - Seed Placement: Minor discomfort, bleeding, infection, bruising
  - MR: Anxiety, stress, claustrophobia
  - Mammography: Anxiety, stress, discomfort
  - Surgical excision of Magseed: Expected discomfort from the operation, bleeding, and infection

**Time Period and Frequency for Event Assessment and Follow-up:** For this study, the study treatment follow-up period is defined as 30 days following the removal of the Magseed. Unanticipated AEs deemed as unrelated or AEs in the mild/grade 1 category do not need to be reported as study data for this study.

**Adverse Event Reporting:** It is the responsibility of the principal investigator to document the grade and attribution of all Adverse Events (AEs) which occur during the course of the study.

The PI will document all AEs that occur within the first 24 hours. AEs will be recoded within the study participant's medical record. The nature of each event, date, time of onset, outcome, frequency, action taken and attribution will be recorded.

**Serious Adverse Event Reporting:** When an adverse event has been identified, the study team will take appropriated action necessary to protect the study participant and then complete the Study Adverse Event Worksheet and log. The principal investigator will evaluate the event and determine the necessary follow-up and reporting required.

**Definition of Unanticipated Problems:** The Office for Human Research Protections (OHRP) considers unanticipated problems involving risks to participants or others to include any incident, experience, or outcome that meets all of the following criteria:

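### The serious adverse event definition joins threat to life and hospital admission in one bullet without an 'or', so a life-threatening event managed without admission does not meet that bullet (minor)

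*Combined protocol and SAP*

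**What the plan says.** Section 9 (Safety Monitoring, Serious Adverse Events) treats an event as serious if, in the investigator's view, "it results in any of the following outcomes". Five bullets follow:

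1. Death.
2. "Life threatening, even if temporary in nature, requiring inpatient hospitalization".
3. Permanent impairment of function or permanent damage to structure.
4. "Necessitates medical or surgical intervention to preclude permanent impairment of a bodily function or permanent damage to a body structure".
5. "Results in an increased level of care (unscheduled admission, transfer from a routine inpatient bed to an intensive care unit, etc".

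Under Severity of AE, the same section associates the severe grade with events that may threaten life, but warns that severe and serious are not the same thing.

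Section 6 (Study Risks) gives the setting: "The Magseed is placed in an axillary lymph node using local anesthesia in an outpatient environment". Among the acute risks it names are damage to vessels or lung during placement, allergic reaction to the wax in the needle, and contrast reactions, of which it says: "Severe allergic reactions to gadolinium are extremely rare and occur in about 1 in 300,000 people".

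**The concern.** Threat to life and need for admission are usually two separate grounds for calling an event serious. Here they share one bullet, with nothing to show that either is enough. The stem makes any one bullet sufficient, but each bullet still has to be met as it is worded.

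This matters because the seed is placed in an outpatient setting, where an acute reaction might be treated and the patient sent home. Section 1 describes the study as a pilot to evaluate safety and effectiveness, so the rule for calling an event serious should give the same answer whoever applies it. As worded, two investigators could classify the same event differently. What is at stake is the consistency of the serious label and of any count built on it.

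**Working it through.** The point rests on wording and the plan gives no figure to reproduce. The check applies each bullet to test cases.

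**Case A: life-threatening event, treated, discharged without admission, no permanent harm.**

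| Bullet | Met? | Reason |
|---|---|---|
| 1. Death | No | Patient survives |
| 2. Life threatening with admission | No, as worded | No admission |
| 3. Permanent impairment or damage | No | None by assumption |
| 4. Intervention to preclude permanent harm | Only by judgement | Refers to permanent harm, not to threat to life |
| 5. Increased level of care | Only by judgement | Both named examples concern inpatient care; the list is open-ended |

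Case A is therefore serious only through a bullet that does not mention threat to life.

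**Case B: life-threatening event with unscheduled admission.** Bullet 2 is met, but so is bullet 5, which lists unscheduled admission. As a joint condition, bullet 2 adds little to bullet 5.

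**Case C: life-threatening event in a patient already in hospital for surgery.** Bullet 2 does not say whether an event during an existing stay counts as requiring hospitalization, and no bullet mentions a prolonged stay. Bullet 5 applies if the level of care rises.

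**What was probably meant.** Two features of the text suggest a drafting slip. Bullet 2 expressly takes in threats that pass, and an admission requirement works against that. Case B also shows that the joint reading leaves the bullet with little to do. A lost 'or' would explain both, although the documents do not confirm it.

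**How often it could arise.** The one rate given is for severe gadolinium reactions, 1 in 300,000 (Section 6). Under Section 5 (MRI), Part 1 scans are non-contrast, and the ten Part 2 women have contrast scans before and after chemotherapy. Section 5 does not say whether the first scan falls after enrolment, so I assume one or two study-period scans per woman:

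- Scans: 10 × 1 = 10, to 10 × 2 = 20.
- Expected severe reactions: 10 / 300,000 = 0.000033, to 20 / 300,000 = 0.000067.
- Equivalently, about 1 in 30,000 to 1 in 15,000 for the whole study.

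No rate is given for the other named risks. Section 6 calls the wax reaction risk very minimal and damage to vessels or lung extremely rare.

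**The case against.** The strongest reply is that little depends on the label, and most of that reply stands.

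- **Other bullets may apply.** A reader might infer that a life-threatening event without admission is excluded from the whole definition. The text does not support that. Bullet 5 turns on an increased level of care and its examples are open-ended, so a move from an outpatient room to emergency care could fit. Bullet 4 could cover some treated reactions. Coverage is uncertain, not absent.
- **Reporting does not wait for the label.** A reader might also infer that reporting and oversight are weakened. Under Serious Adverse Event Reporting, the worksheet, the log and the principal investigator's evaluation start with any adverse event. Section 9 asks for grade and attribution of all adverse events, and Section 10 sends adverse events to the medical record and the database. The exemption from reporting as study data rests on grade and relatedness. Unanticipated problems go to the IRB on unexpectedness, relatedness and greater risk. None of these steps depends on seriousness.
- **No planned safety conclusion turns on it.** One could say that a single relabelled event moves a serious event rate between 1/20 (5%) and 0/20. Section 10 plans no such rate, and the plan sets no safety threshold for one event to cross. The event would still be recorded as an adverse event.
- **The named harms are remote.** Section 4 excludes women allergic to gadolinium or with known wax allergy. The documents do not say that the named reactions would be life threatening, or that they could be managed without admission. Case A is therefore a possibility I have assumed.

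The reply leaves the wording itself untouched. Bullet 2 is an operative rule, it has no 'or', and no other bullet names threat to life.

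**Conclusion.** The bullet is wrong as written, and the error is minor. Read literally, a life-threatening event managed without admission is not serious under the criterion that names threat to life. It is serious elsewhere only if the investigator judges that bullet 4 or the open-ended part of bullet 5 applies.

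The effect is confined to labelling and counting. The contrast calculation suggests that the chance of the gap mattering is very small, but it covers only the one risk for which the protocol gives a rate. The conclusion rests on the plain wording of Section 9 and on the assumption that a life-threatening event could be managed without admission. It would be the same if the cause is a lost 'or', because the text still needs correcting.

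**What to change.** Split the second bullet into two independent criteria. The first keeps the existing words on threat to life, including that it may be temporary. The second covers an event that requires inpatient hospitalization or prolongs an existing hospitalization. The prolongation wording resolves Case C. If the sponsor prefers the smallest edit, inserting 'or' before the hospitalization phrase removes the joint condition but does not address a prolonged stay.

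The stem already makes any one outcome sufficient and needs no change. The cost is one line in a protocol amendment, with no added data, staff or patients and no change to clinical management.

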### Severity of AE:

- Mild – Events require minimal or no treatment and do not interfere with the participant's daily activities.
- Moderate – Events result in a low level of inconvenience or concern with the therapeutic measures. Moderate events may cause some interference with functioning.
- Severe – Events interrupt a participant's usual daily activity and may require systemic drug therapy or other treatment. Severe events are usually potentially life-threatening or incapacitating. Of note, the term "severe" does not necessarily equate to "serious".

### AE relationship to the study intervention:

- Definitely Related – The AE *is clearly related* to the study intervention.
- Probably Related – The AE *is likely related* to the study intervention.
- Possibly Related – The AE *may be related* to the study intervention.
- Unlikely Related – The AE *is doubtfully related* to the study intervention.

- Not Related – The AE *is clearly NOT related* to the study intervention.

**Expectedness:** Principle investigators and co-investigators will be responsible for determining whether an adverse event (AE) is expected or unexpected. An AE will be considered unexpected if the nature, severity, or frequency of the event is not consistent with the risk information previously described for the study intervention.

- Expected Adverse Events
  - Seed Placement: Minor discomfort, bleeding, infection, bruising
  - MR: Anxiety, stress, claustrophobia
  - Mammography: Anxiety, stress, discomfort
  - Surgical excision of Magseed: Expected discomfort from the operation, bleeding, and infection

**Time Period and Frequency for Event Assessment and Follow-up:** For this study, the study treatment follow-up period is defined as 30 days following the removal of the Magseed. Unanticipated AEs deemed as unrelated or AEs in the mild/grade 1 category do not need to be reported as study data for this study.

**Adverse Event Reporting:** It is the responsibility of the principal investigator to document the grade and attribution of all Adverse Events (AEs) which occur during the course of the study.

The PI will document all AEs that occur within the first 24 hours. AEs will be recoded within the study participant's medical record. The nature of each event, date, time of onset, outcome, frequency, action taken and attribution will be recorded.

**Serious Adverse Event Reporting:** When an adverse event has been identified, the study team will take appropriated action necessary to protect the study participant and then complete the Study Adverse Event Worksheet and log. The principal investigator will evaluate the event and determine the necessary follow-up and reporting required.

**Definition of Unanticipated Problems:** The Office for Human Research Protections (OHRP) considers unanticipated problems involving risks to participants or others to include any incident, experience, or outcome that meets all of the following criteria:

- Unexpected in terms of nature, severity, or frequency given (a) the research procedures that are described in the Institutional Review Board (IRB)-approved research protocol and informed consent document. A problem or event is "unexpected" when it occurs at an increased frequency or at an increased severity than expected
- Related to participation in the research. A problem or event is "related" if it is possibly related to the research procedures.
- Suggests that the research places participants or others at a greater risk of harm (including physical, psychological, economic, or social harm) than was previously known or recognized.

**Unanticipated Problem Reporting:** The investigator will report unanticipated problems (UPs) to the reviewing Institutional Review Board (IRB) and lead principal investigator (PI). The UP report will include the following information:

- Protocol identifying information: protocol title and number, PI's name, and the IRB project number;
- A detailed description of the event, incident, experience, or outcome;
- An explanation of the basis for determining that the event, incident, experience, or outcome represents an UP;
- A description of any changes to the protocol or other corrective actions that have been taken or are proposed in response to the UP.

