## 1. PROTOCOL OVERVIEW

**Title:** Evaluation of Magseed as Localization Device for Biopsy Proven Metastatic Axillary Lymph Nodes in Women with Breast Cancer.

**Running Title:** Axillary Magseed Study.

**IRB Protocol Number:** 18-004803.

**Brief Study Description:** Pilot study to evaluate the safety and effectiveness of localizing biopsy proven metastatic axillary lymph nodes in women with breast cancer using Magseed markers as an alternative to the current practice of placing radioactive seed markers.

**Study Population:** Twenty patients with breast cancer will have a Magseed inserted into a biopsy proven metastatic axillary lymph node for pre-surgical localization.

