Phase 2 participants will enroll in the study prior to NAC and have routine contrast enhanced breast MRIs performed before and after NAC. Clinically indicated MRI scans will be charged to the patient's insurance company as this imaging is standard clinical practice. The MRI protocol will use our standard clinical sequences (axial ideal T1 and T2-weighted, axial STIR, and axial 3D vibrant using a dedicated breast coil). Once contrast is injected (gadobutrol 10mmol/10mL) 3D vibrant sequences will be obtained four times after contrast injection (FOV 28 cm or to fit the patient size, and an image-thickness/image-increment of 5mm/1mm).

**Mammogram:** Patients enrolled in the research study will have standard mammographic imaging before and after NAC, which will include both the breast and axilla as per routine clinical protocol.

**Ultrasound:** Patients enrolled in the research study will have standard sonographic imaging before and after NAC of the breast and axilla as per routine clinical protocol. Post-NAC ultrasound of the axilla will be a supplemental assessment to breast MRI as the Magseed artifact may obscure these findings.

**Seed Removal:** As per the current practice, patients will have targeted axillary lymph node dissection including both the localized lymph node and sentinel lymph node. Identifying the lymph node containing the Magseed will require the Sentimag handheld probe in the operating room. This device which functions similar to the gamma probe has been approved for an equipment trial starting in August of 2018. Once the lymph node has been excised a specimen radiograph will be obtained to verify removal.

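### Section 9 lets unanticipated adverse events judged unrelated to an undefined study intervention stay out of the study data, so a new local Magseed signal could be missed

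*Combined protocol and SAP*

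**What the plan says.** Section 1 describes a "Pilot study to evaluate the safety and effectiveness of localizing biopsy proven metastatic axillary lymph nodes in women with breast cancer using Magseed markers". There are twenty women: ten receive the seed after neoadjuvant chemotherapy (Part 1) and ten before it (Part 2). Section 2 gives the length of that chemotherapy as 12-20+ weeks.

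Section 9 defines an adverse event as any untoward occurrence "whether or not considered intervention-related". It then gives one five-level scale, headed "AE relationship to the study intervention", running from definitely related to not related. The intervention is not defined. The principal investigator documents attribution, and the investigators judge expectedness against the risks described earlier, in nature, severity or frequency.

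The follow-up paragraph of Section 9 exempts two classes from study data: "Unanticipated AEs deemed as unrelated", and mild (grade 1) events. This point concerns only the first class. The adverse-events paragraph of Section 10 says that events during the study go into both the medical record and the research database, and states no exemption.

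The expected-event list in Section 9 includes "Surgical excision of Magseed: Expected discomfort from the operation, bleeding, and infection". On the operation itself, Section 5 says: "As per the current practice, patients will have targeted axillary lymph node dissection".

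**The concern.** The exemption selects events when they are collected, and it does so on a judgement of cause. Every participant receives the seed and the investigator knows it. There is no concurrent group to show which local events would have occurred anyway. The judgement is also made against a target that the protocol leaves open: seed, placement, dwell, retrieval, or the whole care pathway.

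The exempted class matters because it consists of events that are not already described, which is where a new device problem would first appear. Part 2 is the most exposed. The seed stays in place throughout chemotherapy, and chemotherapy offers a ready alternative explanation for a local reaction. If the explanation is wrong and the exemption is used, the event is missing from the dataset behind the safety summary. With ten women per part, one missing event is the difference between an observed rate of 10% and one of zero.

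**Working it through.** The plan states no adverse-event rate, safety threshold or derivation of the sample size, so there is no figure to reproduce. The check has two parts.

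**1. The rules side by side**

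| Place | Rule | Depends on relatedness? |
|---|---|---|
| Section 9, definition | Any untoward occurrence is an adverse event | No |
| Section 9, reporting | The principal investigator documents grade and attribution of all events | No |
| Section 9, follow-up | Unanticipated events judged unrelated may be left out of study data | Yes |
| Section 10, adverse events | Events go into the medical record and the research database | No |

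The third row cannot be squared with the fourth. Two coordinators following the protocol in good faith could build different safety datasets.

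The exemption reaches only unanticipated events. Expected events of moderate or worse severity remain reportable even if called unrelated. The described risks are:
- placement (Sections 6 and 9): discomfort, bleeding, infection, bruising, and rare damage to vessels or lung;
- seed (Section 6): allergic reaction and granuloma.

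Section 9's expected list has no entry for the period when the seed is in place, and seed migration is described nowhere. Granuloma is in Section 6 but not in the Section 9 list. An event more severe or more frequent than described also counts as unexpected. So the exempted class is limited but not empty.

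Reporting as an unanticipated problem does not close the gap. All its criteria must be met, and one is that the event is at least possibly related to the research procedures. An event judged unrelated fails that test.

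**2. Scale (assumed rates)**

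Inputs: n = 10 (Part 2, Section 5); r, the true proportion of women with a moderate-or-worse seed-related event; s, the share of those events omitted. Neither r nor s is in the documents.

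P(no event recorded) = (1 − r(1 − s))^10

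| r | s = 0 | s = 0.25 | s = 0.5 |
|---|---|---|---|
| 5% | 0.95^10 = 60% | 0.9625^10 = 68% | 0.975^10 = 78% |
| 10% | 0.90^10 = 35% | 0.925^10 = 46% | 0.95^10 = 60% |
| 20% | 0.80^10 = 11% | 0.85^10 = 20% | 0.90^10 = 35% |

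The share omitted is s = u × m, where u is the share of seed-related events that are unanticipated and m the share of those judged unrelated. Hence s = 0.5 needs u of at least 0.5. With u = m = 0.5, s = 0.25, and the 10% row gives 46%.

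Effect of one omitted event, with exact (Clopper-Pearson) 95% intervals:
- Part 2: 1 of 10 is 10% (0.3% to 44.5%); 0 of 10 is 0% (0% to 30.8%).
- Both parts: 1 of 20 is 5% (0.1% to 24.9%); 0 of 20 is 0% (0% to 16.8%).

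**The case against.** The strongest defence is that the exemption is permissive and the event is not lost. Section 10 sends events to the database, and Section 9 has the principal investigator document all of them and enter them in the medical record. That stands in part: the text permits omission and does not require it, and an omitted event could be recovered from the chart. The adverse-event worksheet and log are a weaker safeguard, because they appear under serious-event reporting and may not be used for a moderate, non-serious event. The defence also leaves the conflict between the two sections unresolved.

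Second, leaving out events that truly are unrelated does not bias a device-related rate. That is correct. Harm requires a wrong attribution, and only for an event outside the described risks. The 50% omission in the illustration is therefore at the high end.

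A reader might also infer that routine surgical complications inflate the Magseed event count, because excision is on the expected list although the operation is current practice. The documents do not support this. Being expected is separate from being related, and the scale allows a rating of not related. Retrieval uses the Sentimag probe, so collecting excision events is reasonable. No Magseed event rate is defined for them to inflate.

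**Conclusion.** The concern holds in a limited form. Section 9 permits a class of events to be left out of the study data on one unblinded attribution to an undefined intervention, in conflict with its own definition of an adverse event and with Section 10. The consequence is that an unexpected local seed event, wrongly attributed to chemotherapy in Part 2, may be absent from the safety dataset.

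The size cannot be fixed from the documents. With r from 5% to 20%, omitting half the events raises the chance of recording none in ten women by 18 to 25 percentage points; omitting a quarter raises it by 8 to 11 points. These figures rest on assumed rates and on events that are both unanticipated and misattributed.

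It would be tempting to call the safety result biased in both directions, or to say that attribution alone decides what is counted. Neither follows. No upward error is shown, moderate-or-worse expected events stay reportable whatever their attribution, and no safety rate is defined against which a net bias could be measured. The change is worth making because it is cheap and removes an avoidable selection step.

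**What to change.** - In the follow-up paragraph of Section 9, remove the unrelated-event exemption for moderate-or-worse events in the ipsilateral axilla, breast, arm or chest wall, and for allergic or infectious events. Record these whatever their attribution, and apply relatedness only at analysis.
- Keep the exemption for other systemic events judged unrelated, so that routine chemotherapy toxicity adds no work.
- Define the study intervention as the seed, its placement, its time in the axilla and probe-guided retrieval, distinct from standard surgery and chemotherapy. Use the same term for unanticipated problems.
- In Section 10, state which events enter the database so that it agrees with Section 9, and plan a table of all-cause and related events side by side, by part.

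A separate rating for every component of care, with a headline from the seed components only, is not needed. It would make the result depend on attribution again.

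The cost is a few sentences of protocol text and a few more local events to enter for twenty women.
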